#### **4.2.8.3 Adverse Events**

All tolerability variables will be summarized using descriptive statistical methods for the SP stratified by treatment regimen and cirrhosis status and overall.

AEs will be coded using MedDRA. A glossary will show the verbatim terms and the corresponding coded terms used (see Table 13).

The number and percentage of patients with treatment-emergent AEs (i.e. any reported event that begins or worsens in severity after initiation of study drug through 30 days post-study drug dosing including those who are related to the study drug independent of the occurrence and those where the date of onset is missing) will be tabulated by primary MedDRA SOC and PT.

Corresponding summary tables will be provided for all serious treatment-emergent AEs and additional for all non-serious treatment-emergent AEs. In the table of non-serious AEs (that must exclude any SAE) only preferred terms that occurred at a frequency of  $\geq 5\%$  in any treatment group will be displayed (no SOCs will be displayed).

The tabulation of the number of patients with treatment-emergent AEs by severity (AEs by severity [mild, moderate, severe], AEs leading to death, AEs leading to hospitalization) and relationship to study drug will also be provided (ABBVIE regimen, ribavirin, medication error -

paritaprevir/r-ombitasvir, medication error – dasabuvir, ABBVIE regimen withdrawn, ribavirin withdrawn).

Patients reporting more than one AE for a given MedDRA PT will be counted only once for that term using the most severe incident for the severity summary table and the most related for the relationship summary table. Patients reporting more than one type of event within a SOC will be counted only once for that SOC.

The frequency of pregnancies will be displayed as well.

#### **4.2.8.4 *Laboratory Data***

All reported clinical laboratory test results will be assigned to one of the time points using the time windows specified in the Table 5. All will be performed for the SP by treatment regimen and cirrhosis status.

Changes from baseline to each post-baseline visit will be summarized descriptively (N, mean, SD, median, minimum, maximum). A summary table will show laboratory hematology. In another table information about clinical chemistry will be summarized.

In a further table CD4 and HIV-RNA are displayed for patients with HIV only by visit.

Instead of the shift tables mentioned in the study protocol, the number and percentage of subjects with post-baseline values until EoT meeting the specified criteria for Potentially Clinically Significant (PCS) laboratory values (defined in Table 11) will be summarized. A post-baseline value must be more extreme than the baseline value to be considered a PCS finding.

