The ABBVIE REGIMEN has been studied with and without RBV in over 2,300 patients in Phase III trials across a variety of patient populations including those with compensated cirrhosis. Based on Phase III data, the ABBVIE REGIMEN, with or without RBV, was well tolerated with a low discontinuation rate. Adverse events (AEs) were typically mild, and many of the AEs and laboratory abnormalities reported were attributable to the presence of RBV. However, these AEs were much milder than observed when RBV was given in combination with interferon. Transient, asymptomatic serum alanine aminotransferase (ALT) elevations were observed at a low rate, were not associated with hepatic dysfunction and generally resolved with ongoing treatment. A disproportionate number of the cases were in women on concurrent systemic ethinyl-estradiol-containing therapy (i.e., contraceptives) and discontinuation of the hormonal therapy with continuation or brief interruption of the ABBVIE REGIMEN led to resolution in serum ALT elevation. Transient elevations in serum bilirubin (predominantly indirect) were observed in subjects receiving the ABBVIE REGIMEN with RBV, related to the inhibition of the bilirubin transporters, organic anion-transporting polypeptides (OATPs) 1B1/1B3, by ABT-450 and RBV-induced hemolysis. Bilirubin elevations occurred after initiation of treatment, peaked by study Week 1, and generally resolved with ongoing therapy. Bilirubin elevations were not associated with aminotransferase elevations. The frequency of indirect bilirubin elevations was lower among subjects who did not receive RBV.

Response of CHC genotype 4 was assessed in the phase II study PEARL-I in which 86 treatment-naïve patients were randomized to the 2 DAA combination of Paritaprevir/r – ombitasvir with vs. without RBV for 12 weeks. The SVR was 100% with RBV vs. 91% without RBV [61]. No serious SAEs or AEs leading to discontinuation were reported.

These results from pivotal studies are encouraging and the new interferon-free regimens might provide physicians with the armamentarium to cure the vast majority of patients

---

Confidential Information

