**Table 4 - Analysis Time Windows**

Phase	Time point	Time Window
Pre-Treatment	Baseline	Last value prior to start of study treatment (i.e. $\leq$ study day 1)
Treatment Weeks	4 (day 29)	Study day during treatment period (Study day 1 = first treatment day) 15 - 42
	8 (day 57)	43 - 70
	12 (day 85)	71 - 98
	16 (day 113)	99 - 126
EoT	Actual EoT	Study day of last dose (28 days prior to EoT - 14 days post EoT)
Post Treatment	4 weeks (28 days post EoT)	8 – 56 post EoT
	12 weeks (84 days post EoT)	57 – 126 post EoT
	24 weeks (168 days post EoT)	127 – 252 post EoT
	48 weeks (336 days post EoT)	253 – 420 post EoT

Mean changes from baseline to each post-baseline visit will be summarized descriptively.

Laboratory data values collected during the treatment period will be categorized as low, normal, or high based on reference ranges used in this study. The number and percent of patients who experience post-baseline shifts during treatment in clinical laboratory values

Confidential Information

No use or disclose outside AbbVie is permitted without prior written authorization from AbbVie  
Version 3.0. (22. Apr 2015) – Germany V3.0 (17. November 2016)

Page 41 of 63

from low/normal to high and high/normal to low based on the reference range will be summarized.

Additional details of the analyses of clinical laboratory data will be specified in the SAP.

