**Table 3 - Analysis Time Windows for HCV RNA**

Phase	Time point	Time Window
Pre-Treatment	Baseline	Last value prior to start of study treatment (i.e. $\leq$ study day 1)
On-treatment		Study day during treatment period^# (Study day 1 = first treatment day)
Treatment Week	4 (RVR*)	15 - 42^
EoT	Actual EoT	Study day of last dose# (28 days prior to last dose - 7 days post last dose)
Post Treatment	12 weeks (SVR 12 window)	$\geq$ 70-126 days post last dose
	24 weeks (SVR24 window)	127-210 days post last dose
	48 weeks (SVR48 window)	> 210 days post last dose

^values must also be  $\leq$  7 days post last dose

#  $\geq$ study day 2

\*RVR = rapid virological response

All reported safety laboratory test results will be assigned to one of the time points using the time windows specified in the table below.

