**Table 4 - Analysis Time Windows for Safety Laboratory Data**

Phase	Time point	Time Window
Pre-Treatment	Baseline	Last value prior to start of study treatment (i.e. $\leq$ study day 1)
Treatment Weeks	4 (day 29)	Study day during treatment period (Study day 1 = first treatment day)
	8 (day 57)	15 – 42 ^
	12 (day 85)	43 – 70 ^
	16 (day 113)	71 – 98 ^
EoT	Actual EoT	Study day of last dose# (28 days prior to last dose - 7 days post last dose)
Post Treatment	4 weeks (28 days post last dose)	8– 56 post last dose
	12 weeks (84 days post last dose)	57 – 126 days post last dose
	24 weeks (168 days post last dose)	127 – 252 days post last dose
	48 weeks (336 days post last dose)	253 – 420 days post last dose

^values must also be  $\leq$  7 days post last dose

#  $\geq$ study day 2

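### Laboratory results from study days 2–14 have no scheduled window although the SAP says all results are assigned, so no planned laboratory summary is designed to show the week-1 bilirubin peak

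*SAP*

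**What the plan says.** **Assignment rule.** SAP 4.2.2 introduces its safety-laboratory windows with "All reported safety laboratory test results will be assigned to one of the time points using the time windows specified in the table below". SAP 4.2.8.4 repeats the rule: "All reported clinical laboratory test results will be assigned to one of the time points using the time windows specified", and names Table 5 as the place. The safety-laboratory windows are printed as SAP Table 4, so that cross-reference is off by one; this does not affect the point.

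**Windows.** Baseline is the last value up to and including study day 1. Protocol Table 4 prints the week-4 window as "Study day during treatment period (Study day 1 = first treatment day) 15 - 42", and the SAP uses the same limits. Weeks 8, 12 and 16 follow at days 43–70, 71–98 and 99–126 in Protocol Table 4. The SAP's EoT window is "28 days prior to last dose - 7 days post last dose", with a footnote that admits values from study day 2 onward. The first post-treatment window covers days 8–56 after the last dose.

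**Summaries.** SAP 4.2.8.4 summarises change from baseline at each post-baseline visit. It replaces the protocol's shift tables with PCS counts over post-baseline values until EoT. The PCS table lists hemoglobin, platelets, ALT, AST, creatinine and creatinine clearance. The CTCAE table lists ALT, AST, hemoglobin and creatinine clearance. Bilirubin is in neither.

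**Expected course.** Protocol 7.1 says of subjects receiving the regimen with ribavirin: "Bilirubin elevations occurred after initiation of treatment, peaked by study Week 1". It adds that the elevations generally resolved on continued therapy. Protocol 9.4.1.2 lists total bilirubin among the tests documented during treatment.

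**The concern.** The rule claims complete assignment, but the table leaves a hole between baseline and day 15. A programmer following the SAP has nowhere to put a day-7 result from a patient who completes treatment, so the value leaves the by-visit tables without any stated decision to drop it.

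The hole covers the one laboratory change that the protocol dates to the first week. The first scheduled post-baseline row is centred on day 29, after a rise that peaked by week 1 could already have receded. For bilirubin no other laboratory table makes up for this. The protocol's shift tables (Protocol 9.7.4) were to use values collected during the treatment period and, as worded, were neither tied to the windows nor limited to particular tests. Their replacement does not include bilirubin. At stake is the laboratory part of the tolerability objective, which is secondary and descriptive. The primary endpoint is untouched, because HCV RNA has its own windows in SAP Table 3.

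**Working it through.** **Inputs.** Baseline: day 1 or earlier. Treatment windows: 15–42, 43–70, 71–98, 99–126 (Protocol Table 4, whose rows are intact; the week-16 limits are not legible in the SAP text as read, which is taken as an effect of reading the PDF). EoT window: last dose L − 28 to L + 7, and not before day 2 (SAP Table 4). Planned courses: 12 weeks (L about day 84) and 24 weeks (L about day 168).

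**Reproducing the plan's windows.** Nominal day − 14 to nominal day + 13:

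| Week | Nominal day | Window |
|---|---|---|
| 4 | 29 | 15–42 |
| 8 | 57 | 43–70 |
| 12 | 85 | 71–98 |
| 16 | 113 | 99–126 |

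All four match. The same rule is not carried back to cover days 2–14, nor forward past day 126.

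**Gap 1.** From day 2 to day 14 is 14 − 2 + 1 = 13 days.

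- L = 84: EoT opens at 84 − 28 = day 56. Days 2–14 are unassigned.
- L = 168: EoT opens at 168 − 28 = day 140. Days 2–14 are unassigned.

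**When EoT reaches back.** A value on day d falls in the EoT window if L − 28 ≤ d, that is, L ≤ d + 28.

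| Day of value | Assigned to EoT if last dose is by |
|---|---|
| 2 | day 30 |
| 7 | day 35 |
| 8 | day 36 |
| 14 | day 42 |

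With L ≤ 30 the whole gap is covered. With L ≥ 43 none of it is.

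**Gap 2.** With L = 168, the days between 126 and 140 are 127–139, or 13 days. The gap closes when L − 28 ≤ 127, that is, L ≤ 155.

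**Calendar share.** 12-week course: 13/84 = 15.5% of treatment days. 24-week course: (13 + 13)/168 = 26/168 = 15.5%. These are shares of days, not of results.

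**After the change.** A Days 2–14 window alone takes the gap from 13 days to 0 in a 12-week course and from 26 to 13 in a 24-week course. A second window from day 127 to the day before EoT opens takes the latter to 0.

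**What the other laboratory summaries recover.**

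| Test | By-visit row for days 2–14 | PCS table | CTCAE table |
|---|---|---|---|
| Total bilirubin | none | no | no |
| Hemoglobin, ALT, AST, creatinine clearance | none | yes | yes |
| Platelets, creatinine | none | yes | no |

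The PCS counts use post-baseline values until EoT, so an extreme early value can count there. The CTCAE text refers to post-baseline or post-nadir visits, and the SAP does not say whether a visit means a windowed time point. If it does, early values drop out there too.

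**The case against.** The strongest case on the other side is that this is a wording slip with little effect.

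- **Early stoppers are covered.** A reader might infer that a week-1 value can appear in no by-visit table. That is wrong: the EoT window takes a day-7 value if the last dose is by day 35. This stands, but it helps only patients who stop early, and it shows their values under EoT.
- **The dated signal is narrow.** A reader might infer a general early toxicity peak, with hemoglobin and ALT changes lost. Protocol 7.1 gives week-1 timing for bilirubin only, in ribavirin recipients, as a transient rise not associated with aminotransferase elevations. Hemoglobin and ALT are in both the PCS and CTCAE tables; what they lose is the early mean change. This stands.
- **The yield may be small.** Only data available from routine practice are collected. The documented values are those closest to windows in a flowchart that is not shown, and nothing establishes that the early on-treatment documentation falls in week 1. So neither a loss of 15% of results nor a flatter reported course is shown. This stands, but an unknown count does not make the assignment rule true.
- **Adverse events offer another route.** An abnormal laboratory finding can be an adverse event (Protocol 11.1), and those are tabulated from the start of study drug whatever the windows. This stands for what investigators report, but it does not summarise the measured values.
- **The second gap is minor.** No described signal is tied to days 127–139, and the gap closes with a last dose by day 155. This stands.

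**Conclusion.** The point holds in a limited form. The SAP's statement that every reported laboratory result is assigned contradicts its own windows. Days 2–14 have no scheduled row for anyone, and all of them are unassigned when the last dose is on day 43 or later. Days 127–139 are also unassigned in 24-week courses with last dose near day 168.

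The material consequence is confined to total bilirubin in ribavirin recipients: no planned laboratory summary is designed to show the peak that the protocol places by week 1. For the PCS tests, only the early mean changes are missing. The size is 13 calendar days per 12-week course and 26 per 24-week course. The number of results cannot be derived from the documents.

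This rests on two assumptions: that the SAP's week-16 window is days 99–126, as in the protocol, and that the table shells in Part II of the SAP, not among the documents, add no bilirubin summary. The change is worth making because the rule cannot be programmed as written and the remedy uses data already collected.

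**What to change.** 1. Add to SAP Table 4 an early on-treatment window for days 2–14, with the existing footnote that values must be no more than 7 days after the last dose. Label it 'Days 2–14' or 'Weeks 1–2', not 'Week 1', because it pools both weeks.
2. For 24-week courses, add a window from day 127 to the day before the EoT window opens.
3. Summarise the maximum on-treatment change from baseline over all values after day 1, regardless of window, at least for total bilirubin. This is the most useful of the three, since it captures the peak wherever it falls.
4. Correct the table reference in SAP 4.2.8.4 so that it points to the safety-laboratory windows.

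The cost is two extra rows in the by-visit laboratory tables, probably with small n, and one additional summary. The layout will also differ from the laboratory tables already produced at the third and fourth interim analyses, which a sentence in the SAP can explain. No new data are needed.

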#### 9.4.1.2 During Treatment Documentation

Follow-up visits are scheduled by the physician per routine clinical practice. Likewise, treatment, procedures and diagnostic methods will follow physicians' routine clinical practice.

The following will be documented:

- Laboratory data

Key clinical chemistry

- ALT
- AST
  
- $\gamma$ -GT
- Total bilirubin
- Creatinine

Remarks

including ULN  
including ULN,  
APRI and FIB-4 will be calculated

creatinine clearance will be calculated

Key hematology

- Hb
- Platelets

Virology

- HCV RNA

quantitative/ qualitative HCV RNA PCR test, see 9.4.1.4

HIV-infected patients only

- CD 4 count
- HIV RNA

most recent assessment  
in copies/mL

- Concomitant medication, see 9.4.1.5
- Adherence to ABBVIE REGIMEN  $\pm$  RBV
- Tolerability (sAEs and AEs, see 11.5) and pregnancies (see 11.6)
- Patient questionnaires see table 2 and 9.4.1.6

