**Table 10 Criteria for PCS laboratory values**

Laboratory data	Very Low	Very High
Laboratory hematology		
Hemoglobin [g/L]	<80	
Platelets [ $10^9/L$ ]	<50	
Laboratory clinical chemistry		
ALT		>5 x ULN and >= 2 x baseline
AST		>5 x ULN and >= 2 x baseline
Creatinine [ $\mu\text{mol}/\text{L}$ ]		>132.605
Creatinine clearance [ $\text{mL}/\text{min}$ ]***	<50	

\*\*\* estimated by Cockcroft-Gault-Formula (see above)

Additionally, for hemoglobin and creatinine clearance, the number and percentage of subjects with a maximum Common Terminology Criteria for Adverse Events (CTCAE) Grade of 0, 1, 2, 3, or 4 (see definitions in Table 12) at any post-baseline visit (regardless of the baseline value) through the end of treatment (i.e., Final Treatment Value) will be summarized. For the liver function tests (LFTs) of ALT and AST, the number and percentage of subjects in with a maximum CTCAE Grade of 0, 1, 2, 3, or 4 (see definitions in Table 12) at any post-nadir visit through the end of treatment (i.e., Final Treatment Value) will be summarized. Note, for these analyses, the nadir is used for reference (including baseline).

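### The SAP replaces the protocol's laboratory shift tables with threshold tables that omit total bilirubin and gives no reason, so no patient count of raised on-treatment bilirubin values remains

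*SAP*

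**What the plan says.** Protocol 9.7.4 states that laboratory values from the treatment period "will be categorized as low, normal, or high based on reference ranges used in this study", and that the number and percentage of patients with post-baseline shifts "from low/normal to high and high/normal to low based on the reference range" will be summarised. It exempts no analyte. Protocol 9.4.1.2 lists "Total bilirubin" among the key clinical chemistry documented during treatment; it is also listed at inclusion (9.4.1.1) and after treatment (9.4.1.3).

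Protocol 7.1 gives the background: "Transient elevations in serum bilirubin (predominantly indirect) were observed in subjects receiving the ABBVIE REGIMEN with RBV". It ascribes this to inhibition of bilirubin transporters "by ABT-450 and RBV-induced hemolysis". It adds that the rises peaked by Week 1, generally resolved on continued therapy, and were less frequent without ribavirin.

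SAP 4.2.8.4 then sets out a different categorical analysis, "Instead of the shift tables mentioned in the study protocol". It counts patients with post-baseline values until end of treatment (EoT) that meet the limits in Table 10, "Criteria for PCS laboratory values" (the SAP text cites Table 11, which holds the CTCAE grades). It also tabulates maximum CTCAE grades. Descriptive changes from baseline by visit are kept.

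**The concern.** Bilirubin is the one laboratory value that loses its planned patient count although the protocol itself describes an effect on it with the studied treatment. That effect is described partly as a frequency: fewer patients affected without ribavirin. A frequency is checked by counting patients, and the replacement tables contain no such count.

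What is at stake is the tolerability description. It is a secondary objective in both documents, and the study's rationale is to see how trial efficacy and safety carry over to routine practice. As the SAP stands, the report could not state how many patients had a raised bilirubin value on treatment, with or without ribavirin, or with or without cirrhosis.

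**Working it through.** No sample-size or power figure is involved. The check sets the analyte lists side by side and then compares the timing of the effect with the visit windows.

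**Step 1: analytes.** The routine measured analytes in Protocol 9.4.1.2 (virology and HIV-only tests left aside), against SAP Tables 10 and 11:

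| Analyte documented on treatment | Protocol shift table | SAP Table 10 (PCS) | SAP Table 11 (CTCAE) |
|---|---|---|---|
| ALT | yes | yes | yes |
| AST | yes | yes | yes |
| Haemoglobin | yes | yes | yes |
| Platelets | yes | yes | no |
| Creatinine | yes | yes | no |
| Total bilirubin | yes | no | no |
| Gamma-GT | yes | no | no |

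Both SAP tables also include calculated creatinine clearance. The PCS table therefore keeps 5 of 7 measured analytes and the CTCAE table 3 of 7. The number with no categorical summary of measured on-treatment values is 7 − 5 = 2: total bilirubin and gamma-GT. The protocol describes a treatment effect only for bilirubin.

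**Step 2: other places bilirubin could be counted.** The SAP names total bilirubin only among the baseline laboratory variables (4.2.6.5), and hyperbilirubinaemia only as a current sign of decompensation at baseline (4.2.6.2). On treatment two routes remain:
- change from baseline by visit, as N, mean, SD, median, minimum and maximum;
- adverse event tables, because Protocol 11.1 lets an abnormal laboratory finding count as an adverse event, if a physician reports it.

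The first has no threshold count. The second is not a summary of measured values.

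**Step 3: timing.** With study day 1 as the first treatment day, the end of Week 1 is about day 1 + 7 = day 8. The first on-treatment laboratory window (Week 4) covers days 15–42, so it opens 15 − 8 = 7 days after that point. A day-8 value could otherwise enter a visit summary only through the EoT window, which in SAP Table 4 starts 28 days before the last dose. That requires a last dose no later than day 8 + 28 = day 36, which is early discontinuation of a 12-week (84-day) course. For a patient who completes treatment, a day-8 value is in no visit window.

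The PCS count is worded as using post-baseline values until EoT. Read that way, a bilirubin row there would pick up a day-8 value wherever one was measured.

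**The case against.** The strongest points on the other side are these.

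- **The change is open and within the SAP's remit.** The SAP declares the replacement, and Protocol 9.7.4 leaves further laboratory detail to the SAP. This stands: it is not a hidden contradiction. The gap is the missing reason and the dropped analyte.
- **Bilirubin is not left unanalysed.** A reader might infer that only mean changes remain and that large individual rises are hidden. The documents do not support that: the maximum is reported, so the largest rise in each window and group is visible. Reported elevations are also counted as adverse events, by severity and by relationship to each drug. What is missing is a count of patients from measured values.
- **Joint reading with ALT.** It is tempting to say that the replacement stops ALT rises from being read together with bilirubin, so that the study can no longer test the background statement that the two were not associated. The protocol's shift tables never crossed the two, and testing that statement is not an objective. The replacement did not cause that limit.
- **Attribution.** The protocol describes the effect for the regimen with ribavirin and ascribes it partly to ribavirin, so it should not be read as an effect of the regimen alone.
- **Data may be sparse.** Bilirubin is scheduled for documentation in each period, but Protocol 9.4.1 and Table 2 record only what routine care provides. A Week 1 value exists only if the physician took one. This stands and limits what any table can yield.
- **A reference limit may be lacking.** The protocol notes the upper limit of normal (ULN) as documented only for ALT and AST. This also stands, but it is not decisive: the protocol's own shift analysis presupposes reference ranges, and the SAP already uses a fixed limit for creatinine.

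**Conclusion.** The point holds in this form: the SAP's threshold tables omit total bilirubin, no reason is given, and no patient-level categorical count of measured on-treatment bilirubin remains. The visit summaries that are left would mostly miss an early peak and cannot show how many patients were affected.

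It is a minor safety-reporting gap. One analyte with a described treatment effect is involved, and the number of affected patients cannot be derived from the documents. Two readings underlie it: that the protocol's general reference to clinical laboratory values includes bilirubin, which it does not name in the shift text; and that Week 1 means about day 8. The documents do not say how fast the rises resolve, so some could still be visible from day 15. SVR12 is not affected.

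**What to change.** Do one of the following:

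1. Keep the protocol's low/normal/high shift table for total bilirubin.
2. Add a total bilirubin row to the PCS table and, if wanted, to the CTCAE table. State explicitly that it uses all available post-baseline values until EoT, including those outside the visit windows.

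Report it by the safety population groups already defined in SAP 4.2.1, which separate patients with and without ribavirin and by cirrhosis status. State which reference is used; because ULN is listed as documented only for ALT and AST, a fixed limit chosen by the sponsor may be needed. Add a sentence giving the reason for replacing the shift tables. A count of patients with raised ALT and raised bilirubin at the same visit would be an optional addition, not a restoration of something planned.

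The cost is one more table row and a limit to specify. Because values come from routine care, the table should show how many patients had a bilirubin value, and the count should be read as incomplete.
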